7.7.1 Recording and Reporting Procedures

A multi-screen adverse event eCRF will be used allowing all adverse events to be submitted through a single reporting mechanism. Serious adverse events will require additional information reported on additional screens within the electronic data capture (EDC) system. Source documents, with subject identifiers redacted, can be scanned and attached to the adverse event form as well. The investigator will treat subjects experiencing adverse events appropriately and observe them at suitable intervals until their symptoms resolve or their status stabilizes.

7.7.2 SAE Recording and Reporting Procedures

Serious adverse events will be recorded on the adverse event case report form (CRF). All centers are obligated to report SAEs within 24 hours of their occurrence and/or the site's knowledge of the event to the Reporting Center. The following attributes will be assigned:

- Description
- Date of onset and resolution (if known when reported)
- Severity
- Assessment of relatedness to test article
- Action taken

[figure not shown]
The site investigator will apply his/her clinical judgment to determine whether an adverse event is of sufficient severity to require that the subject be removed from treatment. If necessary, an investigator will suspend any trial procedures and institute the necessary medical therapy to protect a subject from any immediate danger.

Subsequent review by regulatory health authority(ies), the DSMC, IRB/EC, or the sponsor(s) may suspend further trial treatment or procedures at a site. The study sponsor(s) and the regulatory health authorities retain the authority to suspend additional enrollment and treatments for the entire study as applicable.

A subject may voluntarily withdraw from treatment due to what he/she perceives as an intolerable AE, or for any other reason. If voluntary withdrawal is requested, the subject should be asked to continue (at least limited) scheduled evaluations, complete a study termination form, and be given appropriate care under medical supervision until the symptoms of any AE resolve or their condition becomes stable.

7.7.2.1 Reporting Criteria

Figure 7-1: **Reporting Decisions for Adverse Events**

- 1. Notify the site's investigator.
- 2. Complete and transmit an AE Form through the Internet data entry system. Information regarding a SAE report must be recorded in the subject's medical chart.

ethics board/IRB)

- 3. SAE follow-up reports should include hospital admittance notes, hospital discharge summary, clinical notes, resolution date, treatment and any other pertinent information regarding the event. Reporting should not be delayed in order to provide these documents.
- 4. In the event of a death, the SAE Form must be completed and transmitted along with other supporting data (eg, death certificate, medical notes, etc.).

7.8 **Serious Adverse Event Notification**

7.8.1 Notifying the Sponsor

Submit to the Reporting

Center

Study investigators will provide the Reporting Center with data of all SAEs as defined per the protocol on an ongoing basis.

The CRO Medical Monitor is responsible for notifying the sponsor and will do so simultaneously with the reporting to the clinical database. As noted above, this should be within 24 hours of site awareness of the event.

7.8.2 Expedited SAEs Reporting to Regulatory Health Authorities and DSMC

The sponsor's Medical Monitor will review each SAE report and will determine whether the SAE must be reported to regulatory health authorities on an expedited basis. The final decision for disposition regarding expedited reporting to the regulatory health authorities rests with the sponsor's Medical Monitor. The Study Sponsor and Clinical Research Organization (CRO) will provide the DSMC and the Reporting Center with copies of any expedited SAE reports submitted to regulatory health authorities.

The Reporting Center will provide these expedited reports to the individual site investigators. Events that are serious, related to therapy, and unexpected will be reported to regulatory health authorities within 15 days or for deaths and life-threatening events within 7 days (as per applicable regulatory reporting requirements).

7.8.3 Notifying the Data Safety Monitoring Committee

The Reporting Center will provide the DSMC with listings of all SAEs on an ongoing basis. Furthermore, the DSMC will be informed of expedited reports of SAEs. Periodic reports from the DSMC as to the overall safety of the ongoing study, and recommendations regarding continuation will be sent to the investigators for forwarding to their IRBs/ECs if requested.

Investigational sites are instructed to report episodes of anaphylaxis within 24 hours of their occurrence and/or the sites being notified of the event to the Reporting Center for forwarding to the DMSC if the event is associated with any of the following:

- An emergency room visit;
- Hospitalization;
- More than 2 doses of epinephrine being given as treatment for the same episode;
- Assessment of the anaphylaxis as severe, as defined in Appendix 3.

An initial Anaphylaxis Episode form containing the information known to the site at this time will be transmitted to the Reporting Center. The Reporting Center will then relay to the sponsor and DSMC the individual anaphylaxis reports as they are obtained. The investigational site will supplement the initial Anaphylaxis Episode report with additional information pertaining to an event as it becomes available and will forward the information to the Reporting Center.

7.8.4 Notifying the Institutional Review Board and Ethics Committee

The investigator will ensure the timely dissemination of all AE information, including expedited reports and DSMC safety reviews, to the IRB in accordance with applicable local regulations and guidelines.

7.9 Other Safety Assessments and Precautions

7.9.1 Physical Examination and Vital Signs

Physical examinations will be conducted at visits indicated in **Appendix 1** Schedule of Events. Height and weight will also be recorded at specified visits. Vital signs will be measured, including blood pressure (BP), pulse rate (PR), and body temperature. Except where a full, age

appropriate, physical examination is specifically indicated, a symptom-directed physical exam may be performed.

7.9.2 Prior and Concomitant Medications

Prior and concomitant medications will be duly documented in the CRF.

7.9.3 Pregnancy Testing and Contraception

7.9.3.1 Pregnancy Testing

All female subjects of child-bearing age will undergo a serum pregnancy test at screening and then urine pregnancy test at subsequent visits.

7.9.3.2 Contraception

Subjects undergoing OIT are at increased risk for experiencing allergic reactions and may be at increased risk for experiencing anaphylaxis. Anaphylaxis can cause a dangerous drop in blood pressure; and if this were to occur during pregnancy, it could result in compromised placental perfusion and significant risk to the fetus.

Pregnancy is a time when the mother's immune system undergoes complex and incompletely understood changes that are believed to reduce the risk of a maternal immune reaction directed against the fetus. It is also a time when the fetus's immune system is developing. OIT, at its core, entails repeated stimulation of the immune system to affect changes in its makeup and function. What effects OIT-induced changes in the immune system might have on the course of pregnancy or fetal development are currently unknown. Accordingly, female subjects of child-bearing potential are required to practice effective birth control for the duration of the current study.

Female subjects are to use either:

- A highly effective method of birth control, defined as 1 that results in a low failure rate (ie, less than 1 percent per year) when used consistently and correctly, such as implants, injectables, combined oral contraceptives, some intrauterine contraceptive devices (IUDs), sexual abstinence, or a vasectomized partner; or
- Alternatively, if a highly effective method of birth control is not used, an effective, double barrier method of contraception (eg, male condom with female condom, cervical cap, diaphragm, or contraceptive sponge) may be used.

7.10 Stopping Rules

7.10.1 Overall Stopping Rules

The study will be suspended at any time if a treatment-associated death occurs in a subject on active therapy, or that the second of two subjects is admitted to the hospital, within 6 months of the first, as a direct consequence of dosing with study product. Suspension of the study will entail halting the enrollment of subjects and refraining from any dose increases, but will not entail cessation of dosing unless so directed by the FDA or other regulatory agency, or advised by the DSMC and agreed to by the sponsor. The suspension will not be lifted and dose escalation will not be resumed until the information has been discussed with regulatory authorities and the

regulatory authorities either concur with resumption of up-dosing or direct discontinuation of the study in their jurisdictions.

The DSMC will also be continually reviewing safety data, and can also recommend, in its judgment, halting the study for any substantial imbalance in adverse events, apart from anticipated allergic dosing symptoms.

Aimmune Therapeutics additionally reserves the right to discontinue the study at any time for any reason. The regulatory health authority(ies) and IRBs/ECs will be notified in the event of study discontinuation.

7.10.2 Individual Stopping Rules

Individuals may stop the study at any time if they experience subjectively intolerable adverse events or dosing symptoms. They must halt up-dosing and re-start with a reduced dose if more than 3 days of dosing are missed. Seven or more consecutive days of missed dosing due to non-compliance constitutes an individual stopping rule, as does a significant number of episodes of missed dosing (ie, 3 or more consecutive days on at least 3 occasions) during the Up-dosing Period. Missing 15 or more consecutive days of dosing for any reason also constitutes an individual stopping rules, the reader is referred back to Section 4.3.1.

Occurrence of any of the following will result in the cessation of dosing and the subject being discontinued from the study as an escalation failure nonresponder:

- Failure to accomplish up-dosing of study product after 3 attempts
- Failure to identify a tolerated dose of study product after 3 attempts at dose reduction
- Administration of 3 or more doses of epinephrine for the treatment of any dose-related allergic reaction.

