4.3.1 Criteria

No subject randomized into this trial who discontinues treatment for any reason will be replaced.

Unless required for safety reasons (ie, medical treatment of SAEs), subjects eligible for an Exit DBPCFC will not be unblinded earlier than their scheduled DBPCFC. Subjects who are considered escalation failures will be unblinded no sooner than Week 64 (or when the last subject completes the Exit DBPCFC).

Any subject will be prematurely terminated from additional allergen exposures for the following reasons:

- 1. Life-threatening symptoms (CoFAR Grade 4; refer to **Table A4** in **Appendix 4**), including, but not limited to, anaphylaxis resulting in hypotension, neurological compromise, or mechanical ventilation secondary to peanut OIT dosing or any peanut food challenge
- 2. Severe symptoms (CoFAR Grade 3; refer to **Table A4** in **Appendix 4**), including, but not limited to, those that require intensive therapy (to be determined by the investigator, but may include such interventions as IV epinephrine, intubation, or admission to an intensive care unit) or those that are recurrent

Any subject may be prematurely terminated from additional allergen exposures for the following reasons:

3. Poor control or persistent activation of secondary atopic disease (eg, atopic dermatitis, asthma)

- 4. Started on angiotensin receptor blockers (ARBs), angiotensin-converting enzyme (ACE) inhibitors, beta-blockers, or other prohibited medications, with no alternative medications available per the prescribing doctor
- 5. Pregnancy
- Non-adherence (non-compliance) with home peanut OIT (study product) dosing, as indicated by missing > 7 consecutive days on any 1 occasion, or 3 consecutive days on 3 or more occasions during the Up-dosing Period, as this could constitute a potential safety issue
- 7. Medically indicated circumstances (eg, as part of the treatment for intercurrent adverse events) that require missed peanut OIT (study product) dosing for >14 consecutive days

Any subject may also be prematurely terminated from the study if:

- 8. The subject elects to withdraw consent from all future study activities, including follow-up
- 9. The subject is "lost to follow-up" (ie, no further follow-up is possible because attempts to reestablish contact with the subject have failed)
- 10. The subject develops biopsy-documented eosinophilic esophagitis (EoE)

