6.7.7 Reactions Occurring During the Maintenance Period

This phase consists of the subject receiving the 300 mg/d dose of study product for approximately 24 weeks. For any noted symptoms during the Maintenance Period, the same study product dosing guidelines and procedures will be followed as for the Up-dosing Period.

6.8 Missed Peanut OIT (Study Product) Doses during Up-dosing:

Missed doses of study product at any phase of the study can pose a significant risk to the enrolled subjects, but the risk is believed to be highest during the Up-dosing Period. The algorithm for missed consecutive doses of study product is as follows:

- Miss 1 dose The next dose would be at the current dose level and could be given at home
- Miss 2 doses in a row The next dose would be the current dose level and could be given at home
- Miss 3 doses in a row The next dose would be the current dose and would be given under supervision in the CRC
- Miss 4 doses in a row The next dose would be the current dose and would be given under supervision in the CRC
- Miss 5-7 doses in a row Initiate the next dose at approximately 50% of the last tolerated dose (to the nearest feasible available whole dose that is ≤50% of the last tolerated dose). This dose is to be administered under supervision in the CRC. If tolerated, dose escalation may resume with dose increases of 1 dose level occurring no more frequently than weekly and generally no less frequently than every 4 weeks until the subject has returned to the dose level at which the lapse in dosing occurred. If symptoms occur, the dosing guidelines for the up-dosing period apply.
- Missing > 7 consecutive days of dosing due to non-compliance, ie, for any reason other than treatment of an AE or a study product dispensing error, constitutes an individual stopping rule and the subject is to stop taking study product. The subject will be considered an escalation failure nonresponder, and will be asked to return to the CRC 14 days following their last dose of study product to undergo an Early Discontinuation Visit (Section 6.5).

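### Protocol 7.10.2 contradicts the missed-dose algorithm in 6.8 at exactly 4 missed days and at exactly 7 days missed through non-compliance

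*Protocol*

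**What the plan says.** Section 7.10.2 of the protocol (Individual Stopping Rules) sets two limits for missed doses. On restarting: "They must halt up-dosing and re-start with a reduced dose if more than 3 days of dosing are missed". On stopping: "Seven or more consecutive days of missed dosing due to non-compliance constitutes an individual stopping rule". It then refers the reader back to Section 4.3.1.

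Section 6.8 (missed study product doses) works through consecutive missed doses one count at a time. For 4 in a row it says: "The next dose would be the current dose and would be given under supervision in the CRC". For 5 to 7 in a row, with no limit on the reason, it says: "Initiate the next dose at approximately 50% of the last tolerated dose". Its stopping rule begins: "Missing > 7 consecutive days of dosing due to non-compliance". Such a subject is to stop study product and is an escalation failure nonresponder.

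Section 4.3.1 item 6 defines non-adherence with the same threshold as 6.8: "missing > 7 consecutive days on any 1 occasion". That item stands in the list of reasons for which a subject may, rather than will, be terminated.

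**The concern.** A site that reads 7.10.2 and a site that reads 6.8 would act differently on the same facts. After a 4-day lapse, one must cut the dose and the other gives the full current dose under observation. After a 7-day non-compliant lapse, one takes the child off treatment and the other restarts at about half dose.

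These rules set the next allergen dose for subjects selected because they reacted at or below 100 mg of peanut protein. Section 6.8 itself describes missed doses as a significant risk, highest during up-dosing. The 7-day boundary also reaches the endpoint. A stopped subject has no Exit food challenge and is a nonresponder (SAP 7.4.2), while a restarted subject can still become a responder.

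**Working it through.** **Side-by-side reading.** The check is to take each run of consecutive days missed through non-compliance and read off what each section requires.

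| Consecutive days missed | Section 6.8 | Section 7.10.2 | Result |
|---|---|---|---|
| 1 to 3 | Current dose (in the CRC at 3) | No reduction required | Agree |
| 4 | Current dose in the CRC | Reduced dose | **Conflict** |
| 5 to 6 | About 50% in the CRC | Reduced dose | Agree |
| 7 | Restart at about 50% | Stop | **Conflict** |
| 8 to 14 | Stop | Stop | Agree |
| 15 or more | Stop | Stop | Agree |

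The restart rule in 7.10.2 does not say that the missed days must be consecutive, but four consecutive days fall under it on any reading. The 7-day conflict exists only for non-compliance. A 7-day interruption to treat an adverse event is not caught by the 7.10.2 stop.

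**Size of the dose difference at 4 days.** 7.10.2 gives no size for the reduction. If it means one step of Table 3-2, the ratio of current dose to next lower dose at 6, 12, 20, 40, 80, 120, 160, 200 and 240 mg is 2.0, 2.0, 1.67, 2.0, 2.0, 1.5, 1.33, 1.25 and 1.2. If it means a halving, the ratio is 2.0 throughout. So the two texts differ by a factor of 1.2 to 2.0.

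**Size of the endpoint effect at 7 days.**
- Inputs: 495 children (protocol 9.4) or 499 (SAP 2.4), randomized 3:1, so about 371 AR101 and 124 placebo, or 374 and 125.
- One AR101 child changed from responder to nonresponder: 1/371 = 0.27 points; 1/374 = 0.27 points.
- In expectation, allowing for the chance that the child would have responded: 0.27 × 0.50 = 0.13 points at the planning rate, and 0.27 × 18/23 = 0.21 points at the rate seen in ARC001 completers.
- Illustration at the planning rates of 50% and 20%, taking 186/371 versus 25/124: the Farrington-Manning 95% lower bound is 20.7%. With one AR101 responder lost (185/371) it is 20.4%. With five lost (181/371) it is 19.3%. All exceed the 15% margin. Five is an assumption, since the documents give no count of 7-day lapses.

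**Per Protocol population.** A subject stopped at 7 days has no Exit challenge, so cannot be in the Completer population or in the Per Protocol population drawn from it. A subject restarted under 6.8 has departed from 7.10.2, but is excluded only if blinded review calls that a major deviation that may influence desensitization (SAP 4.4 and 5). SAP 4.4 requires Per Protocol analyses when that population differs from Completers by more than 5% in an arm. If all children complete, that takes floor(0.05 × 124) + 1 = 7 placebo or floor(0.05 × 371) + 1 = 19 AR101 children. Protocol 9.2.3 repeats the analyses in that population without this condition.

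**The case against.** **The effect is small and late.** Section 7.10.2 reads like a summary of rules set out elsewhere. At 4 days the fuller dose is supervised, and the Medical Monitor is available for dosing questions that the protocol does not answer. Enrollment is complete, so few subjects may remain in up-dosing. All of this stands, and it limits the benefit. It does not remove the contradiction: 7.10.2 uses mandatory language, and a site following it is not misreading it.

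**The plan already points to an answer.** A reader might infer that nothing helps a site choose between the sections. The documents do not support that for the 7-day case, because 7.10.2 refers back to 4.3.1, whose threshold matches 6.8. (That sentence is damaged in the available text, so little should be built on its exact wording.) The reference does not help at 4 days, where 4.3.1 is silent on the restart dose. Even at 7 days it leads to an item that permits termination, whereas 6.8 requires it.

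**Severe symptoms.** A reader might also infer a third contradiction. Section 4.3.1 opens a list with "Any subject will be prematurely terminated from additional allergen exposures for the following reasons". Its item 2 names severe symptoms (CoFAR Grade 3), "including, but not limited to, those that require intensive therapy" or that are recurrent. Section 6.7.2 allows continuation at a reduced dose level. Section 6.7.5.1 leaves the decision to the investigator in consultation with the Medical Monitor, with a two-step reduction if the subject continues. The tension is real, but a firm conflict is not shown. Naming recurrent reactions would be largely redundant if any first Grade 3 reaction ended treatment. The severity definitions in 6.7.1 are a general guide applied by judgment, and the Grade 3 text in Appendix 4 is not readable here. This supports a clarification query and no more.

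**Conclusion.** The contradiction is established by reading 6.8 and 7.10.2 together. It occurs at exactly 4 consecutive missed days and at exactly 7 consecutive days missed through non-compliance, and nowhere else on the scale of consecutive missed days. At 7 days, 7.10.2 is the outlier against both 6.8 and 4.3.1.

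The consequence is inconsistent dosing and stopping between sites, with a safety dimension. The tempting stronger reading is that this endangers the primary result or the Per Protocol analysis, and the documents do not support it. The shift is at most 0.27 points per AR101 child. Five assumed cases leave the lower bound well above the margin. Stopped subjects fall outside the Per Protocol population in any case, and deviations already go through blinded review. These figures rest on the planning response rates and an exact 3:1 split of the children. The true number of affected subjects is unknown.

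**What to change.** In 7.10.2, change the restart threshold from more than 3 days to more than 4 consecutive days, and the non-compliance stop from seven or more days to more than 7. Add one sentence stating that 6.8 governs missed doses. In 4.3.1 item 6, align the optional termination with the mandatory stop in 6.8.

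As a separate clarification query, ask the sponsor's medical lead to reconcile 4.3.1 item 2 with 6.7.2 and 6.7.5.1 for a first severe reaction that is neither recurrent nor in need of intensive therapy. Which way to resolve it is a clinical decision.

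The cost is a few lines of text. Under protocol 11.1 an amendment needs ethics and health-authority approval before use, and only subjects still dosing can benefit. No new data are needed.

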6.7.3.2 Assessment of Chronic / Recurrent Symptoms

GI symptoms were the most common potentially allergic symptoms to occur on a subacute, chronic, and/or recurrent basis during Phase 2 clinical trials with AR101. Atopic dermatitis, seasonal allergies, or asthma are other potentially non-acute allergic reactions that could be brought on or exacerbated by OIT. The absence of a clear temporal relationship between dosing

and the emergence of recurrent symptoms may help to distinguish these from acute dosing-related symptoms.

If symptoms arise that suggest a chronic/recurrent reaction to study product, the dose level should be reduced. As with acute symptoms, the level of the dose reduction should be guided by the severity of the symptoms. Symptomatic treatment is permitted (refer to Section 6.7.5), but should be used as a supplement to dose reduction, not a substitute for it.

For chronic/recurrent GI symptoms, especially upper GI symptoms, investigators are advised to have a low threshold for instituting a dose reduction and/or for considering early discontinuation of affected subjects from the study, owing to the potential for EoE.

For subjects determined to be having dose-limiting chronic/recurrent GI symptoms up to and including the 20 mg/d dose level, it is advised that dosing of study product be suspended for 4 weeks and resumed at a dose level of 3 mg/day for a minimum of 4 weeks, with the first dose given in the CRC under medical supervision. If tolerated, up-dosing may resume, with caution, according to the usual schedule, as tolerated, (Note – The 4-week suspension of dosing in response to chronic/recurrent GI symptoms occurring up to and including the 20 mg/d level is the only protocol-specified exception to the rules for missed OIT delineated in Section 6.8.)

For subjects who develop dose-limiting chronic/recurrent GI symptoms at the 40 mg/d dose level or above, dose reduction and re-escalation is to proceed as described in **Section 6.7.5**.

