- Temporarily withholding study product dosing this may be instituted as treatment for an intercurrent AE or to aid the investigator in determining if a dose level is or is not tolerated, but the duration of withholding study product may not exceed 14 consecutive days, or the subject will be discontinued from the study. The manner in which dosing may resume after withholding dosing of study product depends on the duration for which dosing was withheld.
- Reducing dose by 2 dose levels and maintaining the reduced dose level for at least 6 weeks – continuing dosing at a reduced dose level for at least 6 weeks prior to attempting re-escalation is mandatory if 2 doses of epinephrine are given to treat a single AE.
- Stopping dosing and discontinuing the subject early from the study this is an option that the subject may elect at any time and for any reason. The investigator must discontinue the subject from further dosing and continuation in the trial under circumstances that could jeopardize the health of the subject or the integrity of the trial.

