- Additionally, excessive missed dosing, defined as 3 consecutive days of missed doses on 3 occasions during the Up-dosing Period or on 3 occasions during the Maintenance Period, for any reason other than treatment of an AE, constitutes an individual stopping rule and the subject is to stop taking study product. The subject will be considered an escalation failure nonresponder, and will be asked to return to the CRC 14 days following their last dose of study product to undergo an Early Discontinuation Visit (Section 6.5).
- If study product has been withheld for 8 to 14 consecutive days as treatment for an AE or due to a study product dispensing error, dosing may be reinitiated at approximately 25% of the last tolerated dose (to the nearest feasible available whole dose that is ≤ 25% of the last tolerated dose) if the lapse in dosing occurred during the Up-dosing Period. If the lapse in dosing occurred during the Maintenance Period, dosing may, at the investigator's discretion, be reinitiated at 50% of the last tolerated dose (to the nearest feasible available)

whole dose that is \leq 50% of the last tolerated dose). The reduced dose is to be administered under supervision in the CRC. If tolerated, dose escalation may resume with dose increases of 1 dose level occurring no more frequently than weekly and no less frequently than every 4 weeks until the subject has returned to the dose level at which the lapse in dosing occurred. If symptoms occur, the dosing guidelines for the Up-dosing period apply.

If study product has been withheld for ≥ 15 consecutive days for any reason, at any point in the study (with the exception of a dosing hiatus instituted for chronic/recurrent GI AEs at or before the 20 mg dose level, as per Section 6.7.3.2), the subject will be considered an escalation failure nonresponder, and will be asked to return to the CRC 14 days following their last dose of study product to undergo an Early Discontinuation Visit (Section 6.5).

No attempt should be made to make up for a missed dose if greater than 6 hours have elapsed since usual time of dosing.

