7.4.3.2 Gastrointestinal Adverse Events Resulting in Prolonged Disruption of Dosing

Gastrointestinal AEs, typically chronic/recurrent GI AEs, that result in a prolonged disruption of dosing will be considered AEs of special interest and will be assessed longitudinally according to the procedures described below. For the purpose of delineating these AEs of special interest, prolonged disruption of dosing is defined as withholding study product for > 7 days. This will include 3 categories of subjects:

- Any subject whose dose is withheld for > 7 days due to GI AEs and resumes dosing at a reduced dose level (Section 6.7)
- Any subject who develops chronic/recurrent GI AEs at or before reaching the 20 mg dose level and resumes dosing after a 30-day dosing hiatus (Section 6.7.3.2);
- Any subject who permanently discontinues dosing who had experienced GI AEs (Section 4.3.2).

Subjects under the age of 18 years who fall into any of these 3 categories will be asked to fill out the PEESSTM v2.0 questionnaire (Franciosi et al., 2011), with the assistance of a parent or guardian, as appropriate, every month for 6 months; adults will be given the same questionnaire. It should, however, be noted that the PEESSTM v2.0 was not designed to establish a diagnosis of EoE, and has not been validated for use in patients with GI symptoms of other etiologies. Furthermore, the discriminant validity of the questionnaire has not been reported in either longitudinal natural history or interventional studies. For these reasons, the use of the PEESSTM v2.0 to monitor the clinical course of GI symptoms must be considered exploratory. Nevertheless, the PEESSTM v2.0 has shown good content and construct validity (Franciosi et al., 2011; Martin et al., 2015) and so holds promise for being a valuable tool to follow the clinical course of EoE or an EoE-like immune-mediated GI syndrome. Thus, the PEESSTM v2.0, could reveal trends toward symptomatic improvement or worsening that might otherwise go undetected.

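### The exception for the GI dosing hiatus is not carried into Protocol 7.10.2 or the 6.7.5 withholding limit, and the hiatus is given as both 4 weeks and 30 days

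*Protocol*

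**What the plan says.** Four places in the protocol treat the hiatus as something a subject can take and then continue:

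- **6.7.3.2.** For dose-limiting chronic/recurrent GI symptoms up to and including 20 mg/d, "it is advised that dosing of study product be suspended for 4 weeks and resumed at a dose level of 3 mg/day". It describes this as the "only protocol-specified exception to the rules for missed OIT delineated in Section 6.8".
- **6.8.** The rule that classes 15 or more consecutive days of withheld product as an escalation failure nonresponder applies "with the exception of a dosing hiatus instituted for chronic/recurrent GI AEs at or before the 20 mg dose level, as per Section 6.7.3.2".
- **6.7.5.2.** The 4-week hiatus with restart at 3 mg/d is among the actions open to the investigator.
- **7.4.3.2.** One category of GI event of special interest is the subject who "resumes dosing after a 30-day dosing hiatus". Appendix 1 (footnote s) and Appendix 6 repeat this.

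Three places set a limit of about two weeks without the exception:

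- **7.10.2.** "Missing 15 or more consecutive days of dosing for any reason" is an individual stopping rule. The sentence then breaks off grammatically and refers the reader to 4.3.1.
- **6.7.5**, bullet on temporary withholding: "the duration of withholding study product may not exceed 14 consecutive days, or the subject will be discontinued from the study".
- **4.3.1, item 7.** More than 14 consecutive missed days for medical reasons is a ground on which a subject *may* be terminated from further exposure.

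On outcome, Protocol 9.2.1 and SAP 7.4.2 class anyone who does not undergo the Exit DBPCFC as a non-responder.

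**The concern.** The section headed Individual Stopping Rules is a natural place for a site to check whether a subject must stop. As printed, it admits no exception. The 6.7.5 bullet uses equally firm language. A site applying either one literally would stop a subject whom 6.8 expressly allows to continue. Nothing in the protocol says which section takes precedence.

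The consequence reaches the primary endpoint. Two subjects with the same symptoms and the same 4-week interruption could be handled differently at two sites, one stopped and counted as a failure, the other continued with a chance to respond. The inconsistency also bears on safety, because it concerns the subjects for whom 6.7.3.2 asks investigators to keep a low threshold for action on account of possible eosinophilic esophagitis.

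**Working it through.** No sample-size, power or alpha figure depends on this point, so there is no figure in the plan to reproduce. The check is a comparison of passages with some day and week counts.

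**1. Does the hiatus cross the limits?** 4 weeks × 7 = 28 days. The 6.7.5 limit is 14 days (28 > 14), and the 7.10.2 limit is 15 days (28 ≥ 15). In whole days, more than 14 and at least 15 are the same threshold, so 4.3.1 item 7, 6.7.5, 6.8 and 7.10.2 all act at the same point. They differ in force and in whether they carry the exception:

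| Section | Threshold | Force | GI exception |
|---|---|---|---|
| 4.3.1 item 7 | >14 days, medically indicated | permissive | not stated |
| 6.7.5 bullet | >14 days withheld | discontinuation | not stated |
| 6.8 | ≥15 days, any reason | escalation failure nonresponder | stated |
| 7.10.2 | ≥15 days, any reason | individual stopping rule | not stated as printed |

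**2. Can a continued subject still become a responder?** Inputs are the 2-week steps in Table 3-2, the 4-week suspension and minimum 4 weeks at 3 mg/d in 6.7.3.2, and the 40-week cap in 3.2. Take the latest scheduled point, the end of the 20 mg step, with no other delay:

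- 3, 6, 12 and 20 mg: 4 steps × 2 weeks = week 8.
- Hiatus: 8 + 4 = week 12.
- At 3 mg/d: 12 + 4 = week 16.
- 6, 12, 20, 40, 80, 120, 160, 200 and 240 mg: 9 steps × 2 weeks = 18, so the first 300 mg dose is at 16 + 18 = week 34.

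That is 40 − 34 = 6 weeks inside the cap. Adding 24 weeks of maintenance gives week 58, inside the 68-week limit. A continued subject can therefore reach the Exit DBPCFC.

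**3. How does a stopped subject become a non-responder?** Not through the nonresponder wording in 7.10.2, which introduces a separate list of three events that does not include missed days. The route is the absent Exit DBPCFC (Protocol 9.2.1, SAP 7.4.2).

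**4. Length.** It is 4 weeks (28 days) in 6.7.3.2 and 6.7.5.2, and 30 days in 7.4.3.2, Appendix 1 and Appendix 6. The two-day difference does not affect step 1, since 30 days also crosses both limits. It does leave the instruction, and one definition of an event of special interest, stated in two ways.

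**The case against.** The strongest reply is that the protocol already answers the question. The exception is stated in 6.7.3.2 and again inside the 6.8 rule itself, the hiatus is listed in 6.7.5.2, and 7.4.3.2 has a category for subjects who resume after it. On this view 7.10.2 is a summary to which a qualifier was not copied. That is a fair account of what the drafters probably meant, and it means that a reader should not infer an open either/or with nothing to guide a site. It does not remove the conflict in the printed words.

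The 6.7.5 part is weaker than the 7.10.2 part. The bullet covers withholding to treat an intercurrent AE or to help judge tolerability; 6.7.5.3 refers doses withheld for an AE to 6.8, which has the exception; and 6.7.3.2 sends GI cases to 6.7.5 only from 40 mg/d upward. Against that, 6.7.5 introduces its bullets as detailed in its subsections, and one of those subsections permits the 4-week hiatus.

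A reader might also infer that discontinuation is mandatory under 7.10.2. The documents do not establish this. The sentence is visibly broken, so text, including an exception, may have been lost in reading the PDF. The section it points to, 4.3.1, is permissive. On the other side, 6.8 uses the same term, individual stopping rule, for events after which the subject is to stop study product.

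Nor does 6.7.3.2 limit its exception to one section. It says that the hiatus is the sole exception to the missed-dose rules and locates those rules in 6.8.

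Finally, if most affected subjects are on AR101, stopping them would lower the AR101 response rate and so work against the product. That limits the risk of a false efficacy claim but does not make subject handling consistent.

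**Conclusion.** The point holds as an inconsistency in wording that can change how a subject is handled. The GI-hiatus exception in 6.7.3.2 and 6.8 is missing from 7.10.2 as printed and, with less force, from the 6.7.5 withholding bullet. Section 4.3.1 item 7 adds a permissive version, and the length of the hiatus is stated in two ways. It applies to subjects of all ages, not only children. The 7.10.2 part depends on the printed sentence being complete; the 6.7.5 wording and the mismatch between 4 weeks and 30 days do not.

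The effect on the response rate cannot be computed. A reader might be tempted to project it from ARC001, where Appendix 6 reports 4 of 29 AR101 subjects stopping because of recurrent GI events. That figure counts discontinuations, with no dose level given, not subjects with dose-limiting symptoms at or below 20 mg/d. The share arising at those doses, the share of sites applying the literal limit, and the later response rate would all have to be assumed.

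Practical reach is limited. Enrollment was complete at Amendment 4 (Protocol 9.4), and the hiatus belongs to the low-dose steps. What remains is subjects still dosing and the blinded classification before database lock. Correction is worthwhile because it is cheap and concerns both endpoint status and safety handling. No view is taken here on which clinical rule is right.

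**What to change.** - Reconcile Protocol 4.3.1, 6.7.3.2, 6.7.5, 6.8, 7.4.3.2 and 7.10.2 with Appendices 1 and 6, so that all state the same treatment of the GI hiatus and the same length. Keep 6.7.5.2 consistent with them, and repair the broken sentence in 7.10.2. The choice of rule rests with the sponsor and its clinical advisers.
- Apply that single rule to any subject still dosing, through a site memo.
- Apply it also at the blinded pre-lock review (SAP 5, 7.4.4 and 11), when deviations are graded and discontinuation reasons assigned. List in the study report, by arm, the subjects who took the hiatus and those stopped after 15 or more missed days for GI symptoms. The size of the issue would then be known.

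The cost is a protocol clarification, a memo and one listing. No new data are needed, and the primary analysis does not change.
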